7.3 Vital Signs

Vital signs include blood pressure, heart rate, respiratory rate, and temperature.

Values and changes from baseline will be summarized at each scheduled visit with descriptive statistics. Both the change from baseline (defined Section 3.1) and the change from Flare-up Cycle Day 1 (flare-up based) will be presented. If multiple records occur within a post-baseline visit, the first non-missing value will be used.

Potentially clinically significant (PCS) values are predefined criteria/thresholds presented in Table 5. PCS values at baseline and new-onset PCS values post-baseline will be summarized with counts and percentages of subjects or flare-ups as appropriate. Separate analyses will be performed for the non-flare-up treatment visits and the flare-up treatment visits. New-onset PCS values are defined as values that were not PCS at baseline (defined in Section 3.1) and were PCS post-baseline.

Table 5: Potentially Clinically Significant Vital Sign Values

	PCS Low	PCS High
Systolic blood pressure	<86 mmHg or a decrease of ≥ 25 mmHg from baseline	>180 mmHg or an increase of ≥ 25 mmHg from baseline
Diastolic blood pressure	<48 mmHg or a decrease of ≥ 20 mmHg from baseline	>110 mmHg or an increase of ≥ 20 mmHg from baseline
Heart rate	<45 bpm or a decrease of ≥ 20 bpm from baseline	(1) >105 bpm AND an increase of ≥ 20 bpm from baseline (2) >125 bpm

mmHg = millimeters of mercury, bpm = beats per minute.

7.4 Body Weight

Values and changes from baseline for body weight and body weight z-score will be summarized by visit with descriptive statistics for Non-flare-up Treated Population and Flare-up Treated Population. Mean values will be plotted over time.

7.5 Linear Growth Assessment

A linear growth assessment will be performed for subjects under the age of 18 years at the time of enrollment into study with open epiphyseal growth plates using stadiometer and knee height assessments.

Values and changes from baseline (defined as assessment at screening visit in Part C) will be summarized for linear height and knee to heel length by visit with descriptive statistics.

The values and change from baseline for linear height z-score will also be calculated for each scheduled visit.

Z-scores will be obtained from <https://www.cdc.gov/nccdphp/dnpao/growthcharts/resources/sas.htm>.

The following spaghetti plots by chronological age at assessment will be provided:

- linear height and linear height z-scores over time
- Knee height over time

Growth velocity will also be summarized in tables and figures. The calculation of growth velocity will be performed as follows: $((\text{Current Height} - \text{Previous Height}) / (\text{duration (days)} = (\text{current date} - \text{previous date}))) * 365.25 = \text{Annualized Growth Velocity (cm/year)}$. In addition to providing the calculated growth velocities per time period for each subject, the data will also be categorized according to worst growth velocity and last growth velocity by the following three categories: <4 cm/year; 4 to 5 cm/year; and >5 cm/year.

Growth assessments (linear height, knee height, and femur and tibia lengths and growth velocity over 12 months) will also be assessed by age category and premature growth plate closure (PPC) status.

-

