PROMIS Global Health T-score and changes from baseline (defined in Section 3.1) will be summarized at each scheduled visit with descriptive statistics. Data from adult (both physical health and mental health) and pediatric forms will be summarized separately.

7 Safety Data

Safety data summaries in the final CSR will be based on the safety data presentations in recent documents, including the Safety Update included in the NDA and the Day 90 Safety Update; the primary difference will be that those summaries included data from all palovarotene studies, while the Study 202 presentations will only include data collected in Study 202.

While the majority of content listed below corresponds to the data presentation in the interim CSR, it is also relevant for pooled summaries that will be the basis for the final CSR safety discussion.

Adverse events will generally be presented by treatment period (See Section 7.1 for classification of treatment periods) and in total for the Enrolled Population.

The Principal Safety Set (Principal SS) includes all enrolled subjects with the R206H ACVR1 mutation receiving at least one dose of palovarotene in the current study.

Safety data for flare-up based treatment assessments will generally be presented by group combined PVO 20/10 mg for the Flare-up Treated Population.

For vitals, labs, ECGs, physical examination, linear growth assessment and CSSR, summary for non-flare-up based treatment assessments (at regular scheduled visits) will be presented by groups: PVO 20/10 mg only, PVO 5 mg, PVO Total and Never Received PVO Treatment using Enrolled Population. The PVO 20/10 mg only group only includes subjects who did not take PVO 5 mg.

Assessments obtained in Part D include yearly linear height, knee height, weight, physical exam, vital signs, radiographic assessments of the knee and hand/wrist, low-dose WBCT imaging excluding head, adverse events, and concomitant medications.

Pregnancy and Teratogenicity Assessment

Pregnancy and pregnancy outcomes will be monitored throughout the study

Pregnancy test results for females of child-bearing potential were provided as subject listings.

A listing of pregnancy and pregnancy outcomes will summarize subject results

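### Part C SAP 7.5 classes children by the worst height velocity over intervals of any length; where heights are under about 12 months apart, measurement error alone can put a normally growing child in the <4 cm/year class

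*SAP*

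**What the plan says.** All references are to the Part C SAP. Section 7.5 covers subjects enrolled under 18 years "with open epiphyseal growth plates using stadiometer and knee height assessments". It introduces the velocity with "The calculation of growth velocity will be performed as follows": current height minus previous height, divided by the days between the two dates, times 365.25. The output is described as "In addition to providing the calculated growth velocities per time period for each subject", and the length of a time period is not fixed. Each subject is then "categorized according to worst growth velocity and last growth velocity by the following three categories", namely "<4 cm/year; 4 to 5 cm/year; and >5 cm/year".

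The next paragraph of 7.5 plans summaries of "femur and tibia lengths and growth velocity over 12 months" by age category and premature physeal closure (PPC) status. The 12-month span is stated for that breakdown only. Nothing carries it back to the worst and last classes.

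Section 3.6, on unscheduled assessments, covers laboratory tests, vital signs and ECG. It does not mention height, so it does not keep an extra height out of the velocity calculation.

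On timing, Section 2.2 describes annual site visits and 3-monthly remote visits in Part C and refers to the protocol for the schedule of assessments. For Part D, Section 7 states: "Assessments obtained in Part D include yearly linear height, knee height, weight, physical exam, vital signs". The SAP does not say how often height is measured in Part C, nor how precise the measurement is.

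**The concern.** Two features of the rule work in the same direction. Annualising a short interval multiplies any height error by the inverse of the interval in years: a 0.5 cm discrepancy becomes 2 cm/year over 3 months. Taking the worst of several such values then selects the most negative error. The worst velocity therefore falls as heights become closer together or more numerous, even when growth is unchanged.

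Growth is a central paediatric safety question here. Section 1.2 reports a partial clinical hold for PPC in subjects under 14 years, and Part D exists to extend safety follow-up in skeletally immature subjects. A table in which visit frequency alone can move a child into the lowest class can show slow growth that is not there. It can also make real slowing harder to pick out within that table.

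**Working it through.** The SAP gives no figure for this classification, so there is none to reproduce.

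**Inputs from the Part C SAP:** the velocity formula, the worst and last classes and the cut-offs (7.5); follow-up of up to 36 months (2.2).

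**Assumptions, not in the SAP:** constant true velocity v; independent normal error with SD s on each height; equal spacing of d years.

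**Step 1: shortfall needed.** To bring a true 6 cm/year down to 4, the measured increment must fall short by (6 − 4) × d: 0.5 cm over 3 months, 1.0 cm over 6 months, 2.0 cm over 12 months.

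**Step 2: one interval, which is the last-velocity case.** SD of the annualised velocity = s√2/d, and P(<4) = Φ((4 − v)/SD). For v = 6:

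| Spacing | SD, s = 0.3 | P(<4) | SD, s = 0.5 | P(<4) |
|---|---|---|---|---|
| 3 months | 1.70 | 12% | 2.83 | 24% |
| 6 months | 0.85 | 0.9% | 1.41 | 8% |
| 12 months | 0.42 | 0.0% | 0.71 | 0.2% |

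**Step 3: worst of all intervals.** Neighbouring intervals share a height, so the minimum was simulated (200,000 children per setting). Share classed <4 at v = 6 over 3 years:

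| Spacing (intervals) | s = 0.2 | s = 0.3 | s = 0.5 | s = 1.0 |
|---|---|---|---|---|
| 3 months (12) | 39% | 82% | 99% | 100% |
| 6 months (6) | 0.1% | 5% | 41% | 88% |
| 12 months (3) | 0% | 0% | 0.7% | 23% |

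**Step 4: other growth rates over 3 years, s = 0.5, at 3, 6 and 12 months.** For v = 7: 89%, 10% and 0%. For v = 5: 100%, 88% and 23%.

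**Step 5: number of measurements alone.** At 3-monthly spacing, s = 0.3 and v = 6, the share is 68%, 82% and 90% over 2, 3 and 4 years.

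**Step 6: the proposed rule.** Each height is paired with the one 12 months earlier. With v = 6, s = 0.5 and 3 years, the share with worst velocity <4 is 2.1% with 3-monthly heights (was 99%) and 1.2% with 6-monthly heights (was 41%). For v = 5, nearer the cut-off, 54% and 35% remain at s = 0.5, and 8% and about 5% at s = 0.3.

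**The case against.** The strongest objection is that the size depends on a schedule the SAP leaves to the protocol. Section 2.2 describes annual site visits, the 3-monthly visits are remote by default, and 7.5 specifies a stadiometer. Nothing says that height is taken at every remote visit. If heights are yearly, the problem nearly disappears for a child growing 6 cm/year. This stands, and it means the 99% figure is a conditional result and not a forecast. It does not supply the missing interval rule.

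The simulated children also do not represent the whole population. Adolescents near the end of growth may truly grow more slowly than 4 cm/year and would be classed correctly. The percentages are error rates for a child with the stated growth, not expected table entries.

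A reader might infer that the plan as a whole cannot tell slowing from noise. The documents do not support that. Section 7.5 also plans height z-scores with change from baseline, plots of height, z-score and knee height, and 12-month velocity by age and PPC status. Section 7.9.3 adds femur and tibia lengths from whole-body CT, measured by two reviewers. No test or decision rule uses the worst-velocity class.

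A reader might also infer that the move to yearly heights in Part D would look like recovery off drug. For a per-child worst value this does not follow: adding intervals can leave a minimum unchanged or lower it, but cannot raise it. Separate worst-velocity tables for Part C and Part D would be needed, and 7.5 plans none.

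Finally, classes based on 12 months dilute brief slowing around flare-up courses, which last 12 weeks or longer (Section 2.3). This is a real cost, and the reason to keep the shorter-interval velocities in view.

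**Conclusion.** The point holds in conditional form. As written, the rule lets the spacing and number of heights influence a paediatric safety class. Where heights are less than about 12 months apart, measurement error alone can put a normally growing child below 4 cm/year; at 3- to 6-month spacing it often will, depending on the error and on how close true growth is to the cut-off. The last-velocity class is free of the minimum-taking but is also noisy over short intervals.

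The size rests on assumed spacing, error and constant growth. With yearly heights, an error SD of 0.5 cm or less and growth of 6 cm/year, the misclassified share is 1% or less over 2 to 4 years. It is larger for growth near 5 cm/year or an error SD of 1.0 cm. The defect is confined to this classification. It should be corrected before the table is produced, but it does not undermine the other growth analyses.

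**What to change.** In 7.5, derive the worst and last velocity classes only from intervals of about 12 months: for example, pair each height with the one closest to 12 months earlier and accept 10 to 14 months. This matches the span the section already uses for its age and PPC breakdown. Apply the same rule to any Part D velocities that are classed.

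Keep the per-period velocities in the planned tables and figures, each labelled with its interval length. Do not move them to a listing only.

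The cost is SAP wording and programming on heights already collected. There are three downsides. Children with under about 10 months of follow-up get no class. Short slowing around flare-up courses is diluted in the classes, though still visible in the per-period output. And children growing close to 4 to 5 cm/year can still be misclassified, though less often than with shorter intervals.

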7.6 Electrocardiogram

Values and changes from baseline (defined Section 3.1) will be summarized for continuous ECG parameters at each scheduled visit with descriptive statistics. The change from baseline (subject based) will be presented. If multiple records occur within a post baseline visit, the first non-missing value will be used.

Abnormal ECG categories will be assigned based on raw findings as shown in Table 6.

Table 6: Abnormal Electrocardiogram Categories

Abnormal ECG Category	Raw Findings
Rhythm	
 * Atrial premature complexes * Ventricular premature complexes * Sinus arrhythmia * Sinus tachycardia
Conduction	
 * Nonspecific intraventricular conduction delay * Right bundle branch block * Incomplete right bundle branch block * Left posterior fascicular block * Left bundle branch block * Incomplete left bundle branch block
Morphology/Chamber enlargement	
 * Left ventricular hypertrophy * Left ventricular hypertrophy with repolarization abnormality
Axis deviation	
 * Right axis deviation * Left axis deviation

Myocardial infarction	
 * Pathologic Q waves * Acute ST elevation MI * Acute non-ST elevation MI
ST Segment/T Waves/U Waves	
 * Early repolarization * Nonspecific ST and T wave abnormality * Nonspecific ST elevation * Nonspecific U wave abnormalities
Miscellaneous	
 * Long QT interval * Short PR interval

Overall interpretation and abnormal ECG categories will be summarized at each scheduled visit with counts and percentages of subjects or flare-ups as appropriate.

New-onset ECG abnormalities are defined as abnormalities that did not exist at baseline. New-onset ECG abnormalities will be summarized with counts and percentages of subjects or flare-ups as appropriate. A by-subject listing of new-onset ECG abnormalities will be generated.

Incidence of QTc >450 msec, QTc >500 msec, or change from baseline in QTc >60 msec will be summarized with counts and percentages of subjects or flare-ups as appropriate.

Potentially clinically significant (PCS) values are predefined criteria/thresholds presented in Table 7. PCS values at baseline and new-onset PCS values post-baseline will be summarized with counts and percentages of subjects or flare-ups as appropriate. New-onset PCS values are defined as values that were not PCS at baseline and were PCS post-baseline. A listing will be provided for all subjects meeting PCS ECG criteria.

Table 7: Potentially Clinically Significant Electrocardiogram Values

Parameter	PCS Low	PCS High
PR Interval	None	
 1) >200 ms only OR 2) increase from baseline ≥ 20 ms only OR 3) >200 ms and increase from baseline ≥ 20 ms
QRS Interval	None	
 1) >100 ms only OR 2) increase from baseline ≥ 10 ms only OR 3) >100 ms and increase from baseline ≥ 10 ms
QT Interval	None	
 1) >500 ms only OR 2) increase from baseline ≥ 60 ms only OR 3) >500 ms and increase from baseline ≥ 60 ms
QTcF and QTcB Interval	None	
 1) >500 ms only OR 2) increase from baseline ≥ 60 ms only OR 3) >500 ms and increase from baseline ≥ 60 ms

msec = millisecond, QTcF = rate-corrected QT interval using Fridericia's formula (QT interval divided by the cube root of the RR interval), QTcB = rate-corrected QT interval using Bazett's formula (QT interval divided by the square root of the RR interval)

7.7 Physical Examination

Physical examination results and changes from baseline will be summarized at each scheduled visit by body system with counts and percentages of subjects.

7.8 Columbia-Suicide Severity Rating Scale

Suicidal ideation and behavior will be assessed and summarized using the Columbia-Suicide Severity Rating Scale (C-SSRS).

- Type 1-Type 5 suicidal ideation
 - Type 1 suicidal ideation is passive suicidal ideation (wish to be dead)
 - Type 2 suicidal ideation is non-specific active suicidal thoughts
 - Type 3 suicidal ideation is active suicidal ideation without plan or intent
 - Type 4 suicidal ideation is active suicidal ideation with some intent no plan
 - Type 5 suicidal ideation is active suicidal ideation with specific plan and intent
- Behavior
 - Non- suicidal self- injurious behavior
 - Suicidal behaviors include actual attempts, interrupted attempts, aborted attempts, preparatory acts or behavior, and suicidal behaviors

Data listings will be provided for

- All C-SSRS results
- Subjects reporting any type 4 or type 5 suicidal ideations, suicidal behavior or non- suicidal self- injurious behavior

7.9 Bone Safety Data

Bone safety analysis based on WBCT and X-Ray safety imaging data include all phase 2 data (PVO-1A-202 and PVO-1A-201). Additional details can be found in the Bone Safety Management Plan.

Baseline is defined as non-missing measures at first assessed timepoint, regardless of which study this was performed in.

Bone safety data will be described for following time periods:

The Original Baseline Period

The original baseline period will be defined by the original baseline through February 2020.

The Interruption (Off-treatment) Period

The baseline for the off-treatment period is the earlier of the first assessment while off-treatment or the assessment within 1 month prior to the last dose of palovarotene. Bone growth assessments during the interruption period included subjects in the off-treatment population, which was defined as subjects <18 years of age at first study entry who interrupted palovarotene after the clinical hold date and did not re-initiate treatment and who had an off-treatment baseline and post-off-treatment baseline visit.

The end of the interruption period occurred either at the end-of-treatment/end of study visit if the subject discontinued from the study, at the end-of-study visit if they completed the study, at the new baseline if the subject re-initiated palovarotene treatment.

The New Baseline Period

A new baseline was established by the re-initiation of palovarotene dosing following the interruption period. New baseline bone growth assessments includes all subjects who had a new baseline and a post-new baseline visit and received at least one dose of palovarotene after the new baseline visit date. The new baseline visit date was defined as the date of the last visit prior to the re-initiation of palovarotene treatment following the interruption period.

Note that bone safety analysis will also be performed based on premature physal closure status.

7.9.1 Knee and Hand/Wrist Radiographs

Subjects under the age of 18 years at the time of enrollment into Study PVO-1A-202 or PVO-1A-201 with open epiphyseal growth plates will undergo knee and hand/wrist radiographs (AP view) for assessment of epiphyseal growth plate.

Knee and hand/wrist radiographs will be performed remotely (eg, at a local medical facility) for subjects who are unable or unwilling to attend site visits. Once a subject has achieved 100% skeletal maturity (as confirmed by radiography), knee and hand/wrist radiographs will no longer be required.

Summary statistics of bone age and chronological age (values and changes from baseline) for subjects < 18 years will be calculated at each scheduled visit for Enrolled Population. Changes in bone age will be plotted over time.

Two independent radiology reviewers will qualitatively assess the hand/wrist and knee growth plate for abnormalities listed below. Discrepancies in the reads will be adjudicated.

The following abnormalities of the Epiphyseal Growth Plates assessed from X-ray will be assessed:

- EGP Abnormality Location: Wrist or Knee
- Calcinosis
- Cupping
- Dense Metaphyseal Lines
- Frayed Metaphyseal Edge
- Under Mineralisation or Osteopenia of the Adjacent Growing Bone
- Sclerosis of the Adjacent Growing Bone
- Widening of the Epiphyses
- Other

Summary tables of growth plate abnormalities identified in radiographs will include the following:

- Number and percent of subject with epiphyseal growth plates open (by hand/wrist and/or knee).
- Number and proportion of subjects with any abnormality at each visit, for each specific abnormality (e.g. growth recovery lines, Sclerosis, Under mineralization, etc.).
- Number and proportion of subjects with any change from baseline and from prior timepoint for hand/wrist and knee by each abnormality for each visit.
- Number and proportion of subjects with any change from baseline and from prior timepoint for hand/wrist and knee by each abnormality across all post-screening visits. For summaries across all timepoints, the worst case for a given subject will be used in the analysis.
- Number and proportion of subjects with any change from baseline and from prior timepoint for hand/wrist and knee across all abnormalities and post-screening visits. For summaries across all abnormalities and timepoints, the worst case for a given subject will be used in the analysis.

Premature growth plate closure

Listings of all subjects with premature growth plate closure will be provided.

Analyses of Knee Alignment

Distal femoral angle and premature closure of the growth plate will also be summarized for subjects < 18 years old in Enrolled Population.

Summary statistics of lateral distal femoral angles will be calculated for each visit and new-onset potentially clinically significant knee lateral distal femoral angles (i.e. angles outside of the physiological range defined as 78.9 to 84.9 degrees). Listings will also be generated for subjects meeting PCS criteria overall and by PPC status.

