7.9.4 Evaluation of Bilateral Hips by WBCT Safety Read

Although the WBCT scans obtained in the Trial are used primarily to quantify change in HO volume, they will also be used to assess potential adverse effects on the femoral head related to avascular necrosis of the hip (AVN) in all subjects.

Two independent radiology reviewers will qualitatively assess the hip joints on WBCT scan to determine whether there is evidence of AVN. Discrepancies in the reads will be adjudicated. Each hip will be assessed for presence or absence of AVN and by specific abnormalities (i.e. cysts, subchondral lucency, subchondral collapse, osteosclerosis, flattening/collapse femoral head, ...), if present, the degree of change from the baseline scan and previous scan.

WBCT Hip abnormalities identified in WBCT safety reads will be summarized for Enrolled Population include the following:

- Number and proportion of subjects with No, Yes (possible, probable, or definite) AVN or not evaluable at baseline, and by specific abnormality
- Number and proportion of subjects with any new post-baseline or prior time point AVN, and by specific abnormality
- Number and proportion of subjects with any new post-baseline or prior time point worsening in AVN, and by specific abnormality
- Number and proportion of subjects with improvement in baseline or prior time point AVN, and by specific abnormality

Listings of any subject with possible, probable, definite AVN present will be provided.

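### Part C growth-plate change tables state no direction, so new and resolved radiographic abnormalities can add the same count, and the 'worst case' they use has no defined order

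*SAP*

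**What the plan says.** Section 7.9.1 of the Part C SAP lists five summary tables for radiographic growth-plate findings.

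- The second is a prevalence table: "Number and proportion of subjects with any abnormality at each visit, for each specific abnormality".
- The third (by visit) and the fourth (per abnormality over all visits after screening) both begin: "Number and proportion of subjects with any change from baseline and from prior timepoint for hand/wrist and knee by each abnormality". The fifth makes the same kind of count over all abnormalities and visits together.
- The fourth adds: "For summaries across all timepoints, the worst case for a given subject will be used in the analysis". The fifth adds: "For summaries across all abnormalities and timepoints, the worst case for a given subject will be used in the analysis". Neither gives an order of outcomes from worst to best.

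Section 7.9 sets the frame. "Bone safety data will be described for following time periods": an original baseline period, an interruption (off-treatment) period and a new baseline period. The general baseline is the first assessed timepoint, whichever study it came from. The interruption has its own reference: "The baseline for the off-treatment period is the earlier of the first assessment while off-treatment or the assessment within 1 month prior to the last" (the sentence goes on to name the final palovarotene dose). The section also says: "Additional details can be found in the Bone Safety Management Plan". That plan is not at hand.

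Section 7.9.4, on avascular necrosis (AVN) of the hip, gives separate rows for new findings, for worsening, and for improvement: "Number and proportion of subjects with improvement in baseline or prior time point AVN, and by specific abnormality".

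**The concern.** These tables will be read for signs that palovarotene affects the growth plate and for what happens when it is stopped. Section 1.2 records a partial clinical hold for premature physeal closure in subjects under 14. Section 2.2 adds Part D, in which skeletally immature subjects have knee and hand/wrist radiographs one and two years after the last dose. Some films will therefore be compared across a stop in dosing.

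In that setting the direction of a change is what the reader needs. A row that counts change without direction gives one number for two opposite events. The same SAP keeps the directions apart for the hip, and elsewhere defines new-onset laboratory, vital-sign and ECG findings, so the omission in 7.9.1 is not its general style.

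**Working it through.** The plan gives no figure on this point, so there is none to reproduce. The check follows one abnormality through the stated rows.

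**Step 1: one subject.** Code the abnormality 0 (absent) or 1 (present). Assume 0 at the first baseline, 1 at an on-drug visit and 0 at an off-drug visit.

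| Row | On-drug visit | Off-drug visit |
|---|---|---|
| Change from prior film | counted (0 to 1) | counted (1 to 0) |
| Change from first baseline | counted (1 against 0) | not counted (0 against 0) |
| Change from off-treatment baseline, if that film shows 1 | not applicable | counted (0 against 1), within the interruption period |
| Prevalence at the visit | counted | not counted |

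Appearance and resolution add the same count in the first row. Resolution also counts as a change in the third row. The second and fourth rows behave as a reader would wish.

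**Step 2: a group.** Let a share x of subjects gain the abnormality on drug, and a share r of those lose it off drug, with no new findings off drug and the same subjects at every visit. The SAP gives neither value; x = 30% and r = 0.5 to 1 are assumptions.

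- Change from prior film: on drug x = 30%. Off drug r × x = 0.5 × 30% = 15% to 1 × 30% = 30%.
- Change from first baseline: on drug x = 30%. Off drug (1 − r) × x = 15% to 0%.
- Change from an off-treatment baseline that shows the finding: r × x = 15% to 30%.
- Prevalence: 30% on drug, then (1 − r) × x = 15% to 0% off drug.
- New findings off drug: 0% throughout.

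At r = 1 the prior-film row reads 30% in both periods. On drug all of it is new; off drug all of it is resolved.

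**Step 3: what a change count alone can tell.** If a subjects have a new finding and b have a resolved one, the row shows c = a + b. Any a from 0 to c fits the same c.

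**Step 4: the worst case.** The by-visit table has no such rule. In the two across-visit tables, a severity order would presumably place appearance above resolution, but no order is written. A subject whose only change is a resolution still has a change under the stated words. Section 7.9.2 shows that an order can be stated: for open growth plates it lists the categories and selects by their hierarchy.

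**Step 5: comparison with the hip.** Section 7.9.4 has reads that record the degree of change and tables that split by direction. Section 7.9.1 lists the abnormalities to be assessed qualitatively and adjudicated, but mentions no degree. New and resolved can therefore be derived from adjudicated presence or absence. Worsened and improved may not be derivable.

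**The case against.** The strongest reply is that the other planned outputs already show reversal.

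- **Prevalence by visit.** In the example it falls from 30% to between 15% and 0%. Section 7.9.2 likewise gives the frequency of each abnormality at each timepoint on whole body CT. For one abnormality coded present or absent, with the same subjects at both visits, the split can even be recovered. With c = a + b and the rise in prevalence d = a − b, it follows that a = (c + d)/2.
- **Change from the first baseline.** A finding that comes and goes is not counted there once it has gone.
- **The period split.** Off-treatment change has its own period and its own baseline.
- **The worst case.** It presupposes an order, so graded or directional categories are a natural reading of those two tables.
- **Other documents.** The Bone Safety Management Plan may define the change categories. Section 1.2 also sends the combined bone-safety analysis to the integrated safety analysis.

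Much of this stands, and it rules out the stronger readings that a reader might draw. One is that the SAP decides to ignore direction; it is silent on direction, and for the across-visit tables the fault is an undefined order. Another is that evidence of reversibility is hidden, or that recovery would pass for continuing harm; the prevalence table contradicts that. A third is that findings are expected to resolve off drug; the SAP does not say so, and the interruption itself was unplanned. Nor does detection of premature closure depend on these rows, since it has its own listings and summary.

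The reply does not remove the point. The period split separates periods, not directions. The 7.9.1 bullets do not repeat it, two of them pool all visits after screening, and the off-treatment population leaves out subjects who restarted. The recovery by algebra fails when denominators differ between visits, which is likely: percentages use non-missing values (section 3) and films stop at full skeletal maturity (7.9.1). It also fails if changes in degree are counted, and it is not available for the across-visit tables.

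**Conclusion.** The point holds in limited form. In the by-visit change from the prior film, and in change from an off-treatment baseline, a resolved abnormality adds the same count as a new one. The across-visit tables rest on a worst case whose order is not given. Net reversal can be seen at group level from other rows, but the change tables do not separate new from resolved findings within subjects.

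The size depends on how often findings resolve, which the SAP does not say. Under the assumed x = 30% and r = 0.5 to 1, the affected rows read 15% to 30% off drug against 0% new. The conclusion assumes that change is tabulated as worded and that the Bone Safety Management Plan does not already define directional categories. The tables are descriptive and no test depends on them, so this is a question of how clearly safety data are reported. It does not threaten a study conclusion.

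**What to change.** In the three change bullets of 7.9.1:

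- Replace the single count by separate counts of subjects with a new abnormality and with a resolved one, derived from adjudicated presence or absence at each read. Give them for each reference (baseline, prior timepoint) and each 7.9 period.
- Add worsened and improved only where the reads record degree.
- State the worst-case order, for example new or worsened, then unchanged, then improved or resolved. Keep the resolved count as its own row, because a subject can have both a new and a resolved finding over several visits.
- If the Bone Safety Management Plan already defines these categories, cite them in 7.9.1.

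The undirected changes in 7.9.2 for growth plates on whole body CT can be worded the same way.

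The cost is SAP wording and a few more table rows. New and resolved counts need no new images or reads. Worsened and improved counts would need degree to have been recorded, which 7.9.1 does not show.
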